# 1 INTRODUCTION AND RATIONALE

---

## 1.1 BACKGROUND

Medical conditions that require surgical interventions are common worldwide. In the United States alone, there were over 750,000 cardiac and major abdominal surgeries in 2017. The stresses of these surgeries (e.g., prolonged operative time, hypotension, and low blood flow) can lead to complications with lasting effects. One common and serious complication is acute kidney injury (AKI).

Perioperative AKI, marked by signs ranging from a mild decrease in glomerular filtration rate (GFR) to complete renal failure, affects up to 40% of surgical patients and is a leading cause of morbidity and mortality in patients undergoing major surgery. Even AKI that resolves completely is linked to increased risks for hemodialysis, chronic kidney disease, and death years after surgery.

The introduction of the RIFLE (Risk, Injury, Failure, Loss, and End-stage kidney disease) consensus definition of AKI marked the start of recognizing the importance of less severe AKI. RIFLE defines 3 stages of AKI based on at least a 50% change in serum creatinine (SCr) from baseline. The recent KDIGO (Kidney Disease: Improving Global Outcomes) consensus guidelines expand the RIFLE criteria to include creatinine changes as small as 0.3 mg/dl.

AKI is more prevalent in patients in more serious condition and afflicts 55-60% of those admitted to a critical care unit. A single-center cohort study of over 27,000 surgical patients found 37% of patients met the RIFLE criteria for AKI and those patients had a 9x increase in hospital mortality and accounted for 89% of all the post-surgery hospital deaths even though most of them had mild to moderate AKI only.

Even patients whose AKI resolves quickly are at increased risk of requiring hemodialysis, development of chronic kidney disease (CKD) and/or end stage kidney disease (ESKD), and premature death; this increased risk lingering for years after the initial insult. In cardiac surgery patients, moderate AKI doubles length of stay (LOS), hospital cost, and 30-day readmission rates, with severe AKI tripling these same metrics. Hospital mortality is 5x greater for moderate AKI and 11x greater for severe AKI. In a study of more than 36,000 hospitalized patients with baseline GFR over 45 ml/min per 1.73 m^2, one-year mortality for patients who developed AKI (defined as ICD-9 584.xx) without myocardial infarction (defined as ICD-9 410.xx) was 30%. This is more than twice as high as the 14% one-year mortality for patients with myocardial infarction (and without AKI) and is worse than many forms of cancer.

Direct increase of hospital costs in the United States for surgical patients who develop AKI is over \$2.5B per year; secondary costs due to later complications and increased risk of CKD and ESKD (which cost the US \$120B/year) are even higher.

Preoperative risk factors can help identify patients at higher risk of developing AKI. Chief among these are underlying chronic kidney disease and heart failure, along with diabetes, persistent atrial fibrillation and hypertension (among others). Several predictive models have been built

using these risks and other factors. For example, an analysis of the 2018 National Inpatient Survey (NIS) data shows that abdominal and cardiac surgery patients with even one of the risk factors listed above have at least a 30% incidence for AKI (compared to 8% for patients with none of these risk factors).

The goal of preoperative risk stratification is to know when preventative measures should be used during surgery. The current challenge with this approach is that there are few preventative measures to be employed. Apart from the general goals of minimizing bypass and cross-clamp time and minimizing prolonged hypotension, hemodilution, transfusions, and embolic events, very few therapies have been conclusively shown to reduce the incidence of AKI or be protective to the kidneys.

Therapeutic options in the post-surgery period are similarly limited (e.g., avoidance of nephrotoxic agents and hyperglycemia, discontinuation of ACE inhibitors and ARBs, close monitoring of SCr and urine output, and invasive hemodynamic monitoring) and are farther removed from the time of the initial insult.

None of these treatment options address what is frequently the primary cause of AKI: renal ischemia and subsequent reperfusion injury driven by surgery induced hemodynamic perturbations, which are thought to play the largest role in the development of AKI. Studies of noncardiac surgery patients suggest that sustained maintenance of sufficient mean arterial pressure is the most important hemodynamic parameter to preserve in the perioperative period.

Even when focused on hemodynamic maintenance, however, physicians are forced to choose between tools that work against one another. Volume expanders, fluids, and vasopressors can be used to raise mean arterial pressure, but these also reduce flow and increase central venous pressure. Vasodilators can promote flow, but they reduce central pressure.

[figure not shown]
A better approach may be to provide the kidneys with a “perfusion reserve” or “hemodynamic stabilization system” to act as a hemodynamic prophylaxis against AKI by ensuring the kidneys receive adequate pressure and flow during the surgical procedure.

Procyron, Inc. (Procyron) has developed a percutaneous Mechanical Circulatory Support (pMCS) system. The investigational device, the Aortix System, includes an electrically driven micro-pump with an integrated nitinol localization system. The 18F device is deployed trans-femorally to the descending thoracic aorta where its position is maintained by struts that expand to contact the aortic wall. Compared to other percutaneous MCS devices, Aortix has the advantages of not being preload dependent and being located between the heart and kidneys with no part of the system in the left ventricle or crossing the aortic valve.

Once implanted and activated, the Aortix Pump is designed to simultaneously improve renal artery pressure and flow. This “perfusion reserve” may insulate and protect the kidneys against AKI from hemodynamic shocks and generate a renal protective effect through augmented renal perfusion resulting in improved renal function. Aortix also reduces the workload of the heart, which may provide additional benefit during abdominal surgeries or in the immediate period when cardiac surgery patients are off cardiopulmonary bypass. When surgery is complete, the

device is retrieved in the surgical suite or in the catheterization lab, in a procedure that is essentially the reverse of deployment.

The Aortix System has undergone extensive pre-clinical verification and validation studies to confirm device performance and safety requirements following internationally recognized standards and guidance. The Aortix System has also been tested in vivo using large-animal (porcine and ovine) models, successfully demonstrating deployment, retrieval, and acute efficacy. In an ovine microsphere embolization model of heart failure, cardiac afterload (-26%) and cardiac work (-39%) were significantly reduced while cardiac output (+14%) and ejection fraction (+28%) were significantly increased, as were key measures of renal function, GFR (+29%) and urine output (+100%). A separate acute study in a high dose esmolol porcine model of cardiac dysfunction shows how quickly renal artery blood pressure and flow change with pump activation (see Figure 1). The gradual decrease in flow (blue trace) after each step up is evidence of resumed autoregulation by the renal afferent arterioles.

*Figure 1: Renal Artery Pressure and Flow During On-Off Cycles of Aortix Operation*

The Aortix System is currently under safety and effectiveness evaluation in the United States and Australia via a multisite pilot study of patients hospitalized with acute decompensated heart failure who are refractory to medical management with persistent clinical signs of congestion and worsening renal function.

Given the ongoing need to perform operations on high-risk patients and the need to perform lengthy complex surgical procedures, newer strategies are warranted to mitigate surgical risk. Despite advances in surgical techniques, AKI after surgery remains a challenge and newer therapies are needed to reduce the incidence of kidney injury. Along with the investigators, Procyron proposes performing a small (N=20 patients receiving Aortix therapy) feasibility study to evaluate the impact of the Aortix System on AKI incidence and severity in patients

undergoing cardiac surgeries who are at increased risk of developing AKI. In addition, the study will collect data on a control group that does not receive the Aortix System.

## 2 DEVICE DESCRIPTION

[figure not shown]
---

The Procyron Aortix System comprises the Aortix Delivery System, the Aortix Pump, the Aortix Control System, and the Aortix Retrieval System. The Aortix System is investigational. A brief description of each component and a picture follow. Refer to the Aortix System Instructions for Use (PPL004) and Addendum 1 (PPL011) for detailed product specifications and instructions for use.

### **Aortix Delivery System and Introducer Set**

The Aortix Delivery System (ADS) comprises the Aortix Pump positioned inside the Aortix Delivery Tool. The Introducer Set (IS) comprises a sheath and dilator. As described in the Instructions for Use, the Aortix Pump is introduced through the 18F ID / 21F OD sheath.

### **Aortix Pump**

The Aortix Pump is packaged in the Aortix Delivery System. The Aortix pump is an impeller pump that is approximately 6.5cm long and 6mm (18F) in diameter (pump body) and is implanted in the descending aorta superior to the renal arteries via a femoral approach. Expandable struts maintain the position of the device in the descending aorta while the Aortix Pump provides partial circulatory support at a nominal flow of 3.5 liters per minute at a nominal pump speed for 25 krpm. The Aortix Pump has an integral Power Lead (6F in diameter) that exits the arteriotomy and connects to the Aortix Control System. Aortix has no gradient to pump against and uses fluid entrainment to augment pressure and flow in the aorta. In this approach, only a portion of the native blood flow enters the Aortix device. This portion is accelerated by the pump and exits in high velocity jets that entrain, or transfer momentum to, the flow that bypasses the pump. Entrainment allows Aortix to pump effectively while maintaining pulsatile flow. Aortix pumps blood from the aortic root into the abdominal aorta. This decreases aortic root pressure which allows higher cardiac output with reduction in myocardial work. Downstream of the pump, aortic pressure is higher, driving increases in renal perfusion (flow *and* pressure).

### **Aortix Control System**

The Aortix Control System (ACS) comprises the Aortix Cradle and Aortix Controller. The Aortix Controller is connected to the Aortix Pump via an extension Lead, either through the Aortix Deployment Tool handle or through a Power Lead Adapter. The Aortix Controller provides up to approximately 1 hour of battery support when not mounted within the Aortix Cradle and includes alert indicators. The Aortix Cradle is used to

set the Aortix Pump speed, is IV pole mountable, and provides power to the Aortix Controller. The Aortix Cradle displays Aortix Pump operating information and alerts. The ACS version 1.1, 1.2 or 2.0 may be used.

### **Aortix Retrieval System**

The Aortix Retrieval System (ARS) includes (amongst other components) an 18F ID/21F OD Sheath and Dilator. The ARS may be used if the pump remains implanted post-surgery. For the case where the pump is only used during surgery and the sheath remains in place, the only ARS component used is the Retrieval Handle. Either the ARS or the ARS (integrated) systems may be used.

## **2.1 INDICATION FOR USE**

Aortix is indicated as a partial circulatory support device to increase renal perfusion and reduce the incidence of acute kidney injury (AKI) in patients undergoing cardiac surgeries who are at heightened risk of developing AKI.

Currently, the Aortix System is for Clinical Investigational use only, in accordance with this *Clinical Investigation Plan* and subject to required approvals.

## **2.2 PACKAGING/LABELING**

The Aortix Delivery System and pre-loaded Aortix Pump are packaged together within a sterile barrier and placed in a shelf carton. Product labels are affixed to the pouch and the shelf carton; the electronic Instructions for Use (eIFU) document is available exclusively for clinical investigation at: [www.procyrion.com/ifu](http://www.procyrion.com/ifu). The Aortix Introducer Set is packaged separately with an introducer sheath and a dilator. The Aortix Retrieval System components are packaged and labeled in the same way. The non-sterile and reusable Aortix Control System components are packaged together in a foam inset and placed within a shelf carton. Product labels are affixed to the components and the shelf carton and an electronic the Instructions for Use is provided.

All product labels include the statement: “Caution: Investigational Device. Limited by Federal (or United States) law to investigational use. Exclusively for clinical investigations.” This is to comply with United States and international requirements. This device has not been approved for commercial use in any country.

## 2.3 STERILIZATION

The Aortix Delivery System (including the Aortix Pump), Introducer Set, and the Aortix Retrieval System are sterilized by Ethylene Oxide (EO) Sterilization. The Aortix Delivery System, Introducer Set, and Aortix Retrieval System are single-use only and are not to be re-used and are not to be re-sterilized.

The Aortix Control System is packaged in non-sterile packaging. The Aortix Control System components (Cradle and Controller) may be re-used after appropriate cleaning.

## 2.4 SHIPPING/STORAGE

Good Clinical Practice guidelines require accounting for the disposition of all investigational devices received by each clinical site. Information on device disposition consists of the date received, date used, and the patient in whom the device was used. The Investigator is responsible for accounting for all used and unused devices.

The Aortix System will be hand carried or shipped to the sites at intervals dependent on the rate of patient enrollment. The site will be required to account for and document the inventory and study device disposition.

All Aortix System devices for this study must be stored at room temperature in an area free of environmental extremes and with limited, controlled access. Procyrion will inspect the storage area and will ensure study device accountability prior to device use.

Unused product should be returned to the sponsor following final patient enrollment. Expired product can be returned to the sponsor at any time.

# 3 STUDY DESIGN

---

The study is a prospective, non-randomized feasibility study to evaluate the safety and performance of providing support with the Aortix System to patients at heightened risk of acute kidney injury (AKI) undergoing cardiovascular surgery. Patients who decline Aortix system implant or fail to meet anatomical requirements for Aortix implant will be followed in a the non-Aortix arm. Both arms will have the same visit schedule and data collection requirements except for data pertaining to the Aortix system. Data will be reported for both groups.

## 3.1 STUDY OBJECTIVES

### 3.1.1 Safety

- 1) Observe the nature, severity, and frequency of adverse events associated with the delivery and use of the Aortix System

### 3.1.2 Effectiveness:

- 1) Demonstrate a lack of deterioration in post-surgery kidney function
- 2) Reduce postoperative need for advanced renal supportive therapies such as dialysis or renal replacement therapy (RRT)
- 3) Reduce readmission rate secondary to postoperative AKI

## 3.2 STUDY ENDPOINTS

### 3.2.1 Primary Safety Endpoint

- 1) Rate of Occurrence of Serious Adverse Events related to the Aortix implant, retrieval, and therapy (rate will be calculated and reported) [timeframe: enrollment to 30 days post-surgery]

### 3.2.2 Primary Effectiveness Endpoints

- 1) Characterize the change in severity of AKI observed up to 72 hours post-surgery using the KDIGO criteria [timeframe: baseline to 72 hours post-surgery]
- 2) Characterize the rate of postoperative use of renal replacement therapy (RRT), ultrafiltration and/or dialysis [timeframe: Aortix placement to 30 days post-surgery]
- 3) Characterize the rate of 30-day post-surgery readmission due to worsening renal function (if discharged by day 30 post-surgery)

### 3.2.3 Other Data to be Characterized and Reported

- 1) Rate of all adverse events, including death over the course of the study
- 2) Characterize AKI stages as defined by the KDIGO criteria observed postoperatively
- 3) Characterize serum Creatinine changes over the course of the study
- 4) Characterize urine output pre- and post-surgery
- 5) All-cause 30-day post discharge readmissions (if discharged by day 30 post-surgery)
- 6) Characterize the rate of patients remaining hospitalized 7, 14, and 30-days post-surgery.
- 7) Characterize the length of stay in the ICU/CCU and total duration of length of stay in the hospital post-surgery

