### 3.4 STUDY DURATION

It is expected that up to 50 study patients will need to be recruited and enrolled in order to be able to identify and implant 20 patients. Patients who decline to receive the Aortix device or fail anatomical screening and are still planning to undergo surgery, will be offered enrollment in the non-treatment arm of the study. The number of these patients will be capped at 30. Each site should not exceed a 3:2 ratio in terms of non-treatment to treatment patients in order to not exceed the cap.

Patients will be enrolled over a period of approximately one year from time of site activation. The total duration of the patients' participation in the study will not exceed 30 days post the date of surgery.

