#### 4.8.2.4 Every Twenty-Four Hours Post-Surgery ( $\pm$ 6 hours) until Day 7 Post-Surgery or Hospital Discharge (whichever comes first)

1. For patients with Aortix, continue to evaluate Aortix pump access site for bleeding or infection
2. Draw blood to monitor BNP and Serum Creatinine
3. Monitor and report any adverse events or deviations
4. Document medications used and medication changes
5. Record 24-hour urine output and fluid ins
6. Document use of any advanced renal supportive therapies such as dialysis or continuous renal replacement therapy (RRT)
7. Obtain post-operative notes daily, de-identify and provide to sponsor
8. Document any new diagnosis of postoperative Acute Kidney Injury
9. If patient remains hospitalized at day 7, document if prolonged admission is due to AKI (document as adverse event)

Prior to discharge, provide patient instructions for reporting any hospitalizations or device related adverse events. Provide an appointment for the study follow-up discharge visit.

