#### 4.8.2.5 Visit at Day 30 Post-Surgery ( $\pm$ 3 days)

1. Draw blood for monitoring of BNP and Serum Creatinine
2. Document and report any adverse events or deviations
3. If not discharged from index hospitalization by day 30 post-surgery, document if inability to discharge is due to AKI
4. Document and report any rehospitalizations including date and reason for hospitalization
5. Document use of any advanced renal supportive therapies such as dialysis or continuous renal replacement therapy (RRT)
6. Document days spent in ICU/CCU

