## APPENDIX A: SCHEDULES OF DATA COLLECTION

Category	Schedule of Data Collection for Patients with Aortix Removed at the Conclusion of Surgery (Aortix Arm)					
	Pre-Surgery Period (Baseline Monitoring)	Surgery and Aortix Implant	Post-Surgery Monitoring (in Hospital)			Study Exit (Day 30 Post-Surgery)
	Current hospitalization once	Once	24 Hours Post-Surgery (± 1 hour)	At 72 hours Post-Surgery (± 4 hours)	Daily starting at 24 Hours Post-Surgery until Hospital Discharge or Day 7, if still hospitalized (± 6 hours)	Study Exit Visit ± 3 Days
Informed Consent	X					
Anatomy Screening	X					
Med History and Physical Exam	X					
Collect Admission H&P	X					
Weight & Ejection Fraction (EF)	X			X*		
Vital Signs		X	X			
Medications Summary	X	X			X	
Fluid Intake and Urine Output	X	X			X	
Surgical Data with Operative Summary Report and CPB Record		X				
Post Operation Notes		X			X	
Review of AE's, renal replacement therapies	X	X			X	X
Aortix Deployment		X				
Fluoro Image of pump		X				
Required labs (see details App. B)	X		X		X	X
Re-hospitalization, LOS data						X

\*Document the most recent EF recorded post-surgery (if available). Acceptable if it is out of the window.

Category	Schedule of Data Collection for Patients with Aortix Removed in a Separate Procedure Post-Surgery (Aortix Arm)						
	Pre-Surgery Period (Baseline Monitoring)	Surgery and Aortix Implant	Aortix Retrieval Post-Surgery	Post-Surgery Monitoring (in Hospital)			Study Exit (Day 30 Post-Surgery)
	Current hospitalization once	Once	Once	24 Hours Post-Surgery (± 1 hour)	At 72 hours Post-Surgery (± 4 hours)	Daily starting at 24 Hours Post-Surgery until Hospital Discharge or Day 7, if still hospitalized (± 6 hours)	Study Exit Visit ± 3 Days
Informed Consent	X						
Anatomy Screening	X						
Med History and Physical Exam	X						
Collect Admission H&P	X						
Weight and Ejection Fraction (EF)	X				X*		
Vital Signs		X		X			
Medications Summary	X	X				X	
Fluid Intake and Urine Output	X	X	X			X	
Surgical Data with Operative Summary Report and CPB Record		X	X				
Post-Operation Notes		X	X			X	
Review of AE's, renal replacement therapies	X	X	X			X	X
Aortix Retrieval			X				
Fluoro Image of pump		X	X				
Required labs (See details App. B)	X			X		X	X
Re-hospitalization, LOS data							X

\*Document the most recent EF recorded post-surgery (if available). Out of window measurement acceptable (not a deviation) for EF.

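### Section 3.2.3 item 5 promises a 30-day post-discharge readmission measure, but follow-up stops about 30 days after surgery, so the count is truncated against its label (minor)

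*Protocol*

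**What the plan says.** Section 3.2.3, item 5, reads "All-cause 30-day post discharge readmissions (if discharged by day 30 post-surgery". The window is counted from discharge. The parenthesis admits anyone discharged up to day 30 after surgery.

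The follow-up runs on a different clock:

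- Section 3.4 states that a patient's "participation in the study will not exceed 30 days post the date of surgery".
- Section 4.8.2.5, the day 30 (±3 days) visit, is where sites are to "Document and report any rehospitalizations including date and reason for hospitalization".
- In all three Appendix A schedules (two for the Aortix arm, one for the non-Aortix arm), the row "Re-hospitalization, LOS data" is marked only in the study exit column.
- Section 4.8.2.4 adds: "Prior to discharge, provide patient instructions for reporting any hospitalizations or device related adverse events". No contact is scheduled after the exit visit.

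Primary effectiveness endpoint 3 in section 3.2.2 carries the same parenthesis but counts from surgery: "Characterize the rate of 30-day post-surgery readmission due to worsening renal function (if discharged by day 30 post-surgery".

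**The concern.** A 30-day post-discharge readmission figure is normally read as 30 days of observation for each discharged patient. Here each patient contributes whatever is left between discharge and the exit visit, so the item can miss readmissions inside its named window and cannot add any.

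The shortfall in observed days grows with length of stay. Section 1.1 says that moderate AKI doubles, and severe AKI triples, both length of stay and 30-day readmission rates. On the protocol's own account, then, the patients with more severe AKI would tend to have both the higher readmission risk and the shorter observation. Section 3 has data reported for both groups, and section 9 says the results will feed later trial design. A reader could set the two groups' figures side by side, or compare one with an outside post-discharge rate, without seeing that the observation time differs.

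**Working it through.** The protocol states no figure for this item, so there is nothing to reproduce. The check is arithmetic on the windows.

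**Inputs**

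- Labelled window: 30 days from discharge (section 3.2.3, item 5).
- Exit visit day V: nominally 30, permitted range 27 to 33 (section 4.8.2.5 and Appendix A).
- Discharge day d, counted from surgery. The protocol gives no expected length of stay, so the values of d are assumptions. Days 7, 14 and 30 are borrowed from item 6 of the same section, "Characterize the rate of patients remaining hospitalized 7, 14, and 30-days post-surgery". Those are landmark days for the proportion still in hospital, not stay lengths. Days 3 and 4 are added to locate the boundary.

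**Formulas**

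- Observed post-discharge days = V − d, not below 0 and not above 30.
- Day on which the labelled window closes = d + 30.
- The full window is observed only if V − d ≥ 30, that is, d ≤ V − 30.

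**Results**

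| Discharge day d | Observed, V = 30 | Range, V = 27 to 33 | Window closes | Days past the latest visit (day 33) |
|---|---|---|---|---|
| 3 | 27 | 24 to 30 | day 33 | 0 |
| 4 | 26 | 23 to 29 | day 34 | 1 |
| 7 | 23 (77% of 30) | 20 to 26 | day 37 | 4 |
| 14 | 16 (53%) | 13 to 19 | day 44 | 11 |
| 30 | 0 (0%) | 0 to 3 | day 60 | 27 |

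**Boundary.** With V = 30, the full window needs d ≤ 0. With the latest visit, V = 33, it needs d ≤ 3. With the earliest, V = 27, it needs d ≤ −3, which is impossible. So no discharge from day 4 onward gives the full window at any permitted visit date. For discharge on days 1 to 3 it needs a visit after day 30, which the section 3.4 limit does not allow.

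**Between groups.** For the same visit day, the difference in observed days equals the difference in discharge day. If one group typically left on day 7 and the other on day 14 (assumed), they would have 23 and 16 days at risk, a gap of 7 days.

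**The case against.** The best defence is that the item is loosely worded rather than wrong. The parenthesis makes sense if the window closes at day 30 after surgery, and endpoint 3, section 3.4, the exit visit and all three schedules use that clock. Read that way, the item already means readmissions after discharge up to the day 30 visit. That is probably the intention, but the parenthesis only settles who counts. It does not say how long they are observed, and it admits a patient discharged on day 30 who has no post-discharge time at a nominal visit. A later analysis plan could define a denominator, but it could not lengthen the follow-up fixed here.

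The defence is right on weight. Item 5 is not a primary endpoint. Section 9 says that patients are reviewed individually and that the study is not powered. Readmissions up to exit are captured with date and reason.

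Several stronger readings are not supported:

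- *The readmission data are lost or void.* They are truncated, not lost.
- *A known share of readmissions is missed, or the arms are biased.* The arithmetic concerns days observed. The protocol gives neither expected stays nor readmission rates, so the number missed and any difference between groups are unknown.
- *Primary endpoint 3 fails in the same way.* Its clock starts at surgery and its window ends at the planned visit. An early visit leaves at most 3 days uncovered.
- *Primary endpoint 2 cannot be computed in the non-Aortix arm, because its bracket reads* "timeframe: Aortix placement to 30 days post-surgery". That start does not exist in the non-Aortix arm. However, the endpoint counts postoperative use and placement happens during surgery (section 4.5), so a start at the end of surgery gives the same postoperative count. Appendix A has renal replacement therapy reviewed at surgery and afterwards in both arms. This is a wording matter only.

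**Conclusion.** The point holds as a minor labelling error. Item 5 names a window that section 3.4 and the collection schedule cannot deliver for any discharge from day 4 onward, whatever the expected stay. The shortfall for a given patient depends on the discharge day: 7 of 30 days for discharge on day 7, 14 of 30 on day 14, and all 30 on day 30, at a nominal visit. Those discharge days are assumptions; the boundary at day 4 rests only on the protocol's own visit window. Unequal observation between the two groups follows only if their stays differ, which the protocol does not predict. No hypothesis test or primary endpoint is put at risk.

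**What to change.** Relabel item 5 as *all-cause readmission from index discharge to day 30 post-surgery*. Report it with the number discharged and the days at risk, counted to day 30 or to the exit visit, death, withdrawal or loss to follow-up if earlier.

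The cost is one wording edit. Length of stay (section 3.2.3, item 7), readmission dates (section 4.8.2.5), death reports (section 8.1) and withdrawal and study exit records (section 3.5) are already collected, so no visit, test or form is added. The drawback is that the figure can no longer be set against external 30-day post-discharge rates, but the current follow-up could not support that comparison anyway. Keeping the post-discharge window would instead mean contact up to day d + 30 (day 37, 44 or 60 in the examples) and a change to section 3.4.

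Two editorial edits can go in at the same time. Give the endpoint 2 timeframe a start that exists in both arms, for example the end of cardiac surgery, which leaves the postoperative count unchanged. Make the section 3.4 limit agree with the ±3-day exit window.
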